## **A Motivational Training Program for Secondary Physical Education Teachers Based on the Circumplex Model: A Study Protocol of a Randomized Controlled Trial.**

### **Abstract**

**Introduction:** In most Self-Determination Theory (SDT) research, improving (de)motivating teaching styles enables numerous benefits for students and teachers, although there is less evidence on the latter. Although the recent circumplex model provides a fine-grained picture of the different (de)motivating teaching styles (i.e., autonomy support, structure, control, and chaos) that physical education (PE) teachers can use in their lessons, no previous motivational training programs have been based on this model. Moreover, all SDT-training programs have been implemented through different group sessions, but individual sessions have not also been delivered.

**Objective:** This study outlines the protocol of a motivational training program, derived from the circumplex model, designed to enhance (de)motivating teaching styles among PE teachers. Consequently, this program seeks to improve motivational variables and influence (mal)adaptive outcomes in both teachers and students.

**Design:** A randomized controlled trial design with a mixed-method approach.

**Participants:** At least 16 secondary PE teachers will be assigned to either an experimental group or a control group, together with part of their students.

**Intervention:** The training program comprises four face-to-face group sessions and two follow-up sessions (one individual and one group sessions). PE teachers will learn how to support autonomy and provide structure, as well as to be less controlling and chaotic towards students. Over a period of approximately five months, teachers will implement these motivational strategies during their PE classes.

**Outcome measures:** Different (de)motivating teaching styles, motivational variables, and (mal)adaptive outcomes will be assessed in both PE teachers and their students at three distinct

points: before the training program (T1), during the intervention (T2) and at the end of the intervention (T3). Additionally, two discussion groups involving all experimental PE teachers will be held (one following the training program and another at the end of the intervention).

**Conclusion:** The results from this study could be useful for developing motivational training programs for in-service PE teachers.

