### ***Participants and recruitment***

At least 16 secondary PE teachers, eight in the experimental group and eight in the control group, along with their respective students, will be expected to participate in this study. The maximum number of participating teachers will be capped at 20, due to the limited human resources of the research team. PE teachers will select at least two classroom groups comprising at least 14 students each to invite to participate in this study. Eligible students will be those aged 12 to 17 years in secondary schools. Participation will be voluntary and anonymous.

Various social media platforms (i.e., Instagram, Twitter, and WhatsApp) and other communication methods (i.e., email) will be used for teachers' recruitment. An informative poster will be launched, detailing the target sample, content, aims, and training program dates. This poster will also include two links (QR code): one with a document providing further information and another to registration through a brief Google Forms questionnaire. Regarding the additional information document, it is important to note that it will detail a more comprehensive overview of the objectives, the different phases of the program, inclusion criteria, the requirements that each teacher must accept to participate, and the

teaching skills that will be developed during the training program. Teachers with further inquiries can contact the research team via email or phone. The registration period will last approximately 21 days.

Once the interested PE teachers have registered, various inclusion criteria will be considered for the final selection: 1) Being an in-service PE secondary school teacher for the entire academic year; 2) Attending 100% of the training program sessions; 3) Fill in a short questionnaire at the end of each session of the training program, as well as fulfilling questionnaires of the study variables three times; 4) Allowing the recording of two PE lessons; 5) Participating in two focus groups, one at the end of the training program and one at the end of the study, and 6) Not participating in other training sessions related to PE instruction during the program. Moreover, the inclusion criteria for students will be: 1) Authorization from parents or legal guardians; 2) Completion of questionnaires of the study variables three times; 3) Regular participation in PE lessons.

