### ***Focus groups***

Two discussion groups with all PE teachers will be held throughout the study (See Figure 1). Firstly, one focus group will be done immediately after the end of the fourth session of the training program. The main themes covered in the focus groups will be (1) the content of each session of the program (i.e., theoretical background, design of motivational strategies in different teaching units, and implementation of different PE lessons), (2) the didactical approach (e.g., images, videos, practical examples, formative assessment, and interactive exercises) and their perception of (de)motivating teaching style from de trainers (i.e., congruent teaching), (3) perceived changes in beliefs about (de)motivating teachers styles, the satisfaction of their basic psychological needs, and (de)motivating teaching styles towards students, and (4) overall assessment of the training (e.g., innovation, practical usefulness, feasibility of the motivating strategies, intention to implement the motivating strategies, satisfaction, etc.). This last question will complement the short questionnaire completed by the PE teachers at the end of each training program session (see above).

The second focus group will take place at the end of the intervention, coinciding with the completion of the teachers' and students' questionnaires in the post-test (T3). This will make it possible to find out the teachers' perception of the implementation phase, as well as of the different study variables. The main themes covered in the focus groups will be (1) the follow-up of the training program (e.g., individual and group sessions), (2) perceived changes in beliefs about (de)motivating teachers' styles, satisfaction of their basic psychological needs, (de)motivating teaching styles towards students, and job satisfaction, emotional exhaustion, and job performance.

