### **Control group**

Control group teachers will not initially receive the training program and, as a result, will not intentionally implement any motivational strategy. They will only complete the questionnaires at the same times as experimental group teachers (See Figure 1). Control group teachers will receive the training program after the last study measurement, as well as an extensive final report on their teaching profile, and a series of motivational strategies aimed at enhancing their (de)motivating teaching style.

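### Several teacher inclusion criteria describe conduct after randomisation that, up to T3, only the experimental arm can fail; enforced as worded, they would select on adherence in one arm

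*Protocol*

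**What the plan says.** The protocol's section Participants and recruitment sets six inclusion criteria for teachers, considered for final selection after registration. Four of them concern what teachers do during the study:

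- Criterion 2: "2) Attending 100% of the training program sessions".
- Criterion 3, first half: "3) Fill in a short questionnaire at the end of each session of the training program". Its second half reads "as well as fulfilling questionnaires of the study variables three times".
- Criterion 4: "4) Allowing the recording of two PE lessons".
- Criterion 5: taking part in two focus groups, one when the training ends and one when the study ends.

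The section Context, design, and randomization says that teachers who agree to take part are randomly assigned to one of the two arms. The section Control group says of control teachers: "They will only complete the questionnaires at the same times as experimental group teachers", and "Control group teachers will receive the training program after the last study measurement". The Observation section plans lesson recordings for experimental teachers only.

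On the focus groups, the Abstract says "two discussion groups involving all experimental PE teachers will be held", while the Focus groups section says "Two discussion groups with all PE teachers will be held throughout the study".

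**The concern.** An inclusion criterion should be something that can be settled before allocation and that applies alike to both arms. Attendance, session questionnaires and focus-group participation can be observed only after allocation and, on the protocol's own description of the control arm, only among experimental teachers.

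If a teacher who misses a session is treated as not meeting the criteria, that teacher and at least two classes leave the experimental arm. No control teacher can be lost on the same ground. A more committed subset of experimental teachers would then be compared with all control teachers. Missing sessions plausibly goes with workload, motivation and engagement, which lie close to the teacher outcomes measured (need satisfaction, exhaustion, job satisfaction, teaching style), so the distortion would probably favour the program. H2 and H3 both rest on this comparison.

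**Working it through.** **Which criteria can be failed, by whom, up to T3**

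| Criterion | Experimental | Control | Basis |
|---|---|---|---|
| 2, attendance | yes | no | Control group: trained after the last measurement |
| 3, session questionnaires | yes | no | same; no sessions before T3 |
| 3, study questionnaires at T1, T2, T3 | yes | yes | Control group: completed at the same times |
| 4, recordings | yes | no | Observation: experimental teachers only |
| 5, focus groups | yes | no | Abstract: experimental teachers only; Control group: questionnaires only |
| 6, no other PE training | yes | yes | no restriction by arm |

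The asymmetry therefore covers criteria 2, 4 and 5 and the first half of criterion 3. The second half of criterion 3 binds both arms. The second focus group coincides with T3 rather than preceding it, so the exact statement is before or at T3.

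**Possible size.** The protocol gives no attendance rate, so there is no figure of its own to reproduce. Inputs from the document: 8 experimental teachers as the minimum (Participants and recruitment), and 4 group sessions plus 2 follow-up sessions, 6 in all (Abstract). Assumptions: per-session attendance p, independent between sessions.

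- Probability that a teacher attends all k sessions: q = p^k.
- Expected number of 8 who fail: 8 × (1 − q).
- Probability that at least one of 8 fails: 1 − q^8.

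| p | k | q | expected to fail, of 8 | P(at least one fails) |
|---|---|---|---|---|
| 0.98 | 6 | 0.886 | 0.9 | 62% |
| 0.95 | 6 | 0.735 | 2.1 | 92% |
| 0.90 | 6 | 0.531 | 3.7 | 99% |
| 0.98 | 4 | 0.922 | 0.6 | 48% |
| 0.95 | 4 | 0.815 | 1.5 | 81% |
| 0.90 | 4 | 0.656 | 2.8 | 97% |

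For controls the corresponding number is 0 of 8 at every p, because they have no session to miss before T3. Each experimental teacher excluded is 1/8 = 12.5% of the arm at its minimum size.

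**The case against.** The strongest reply is that these are commitments. The criteria are considered after registration and for final selection, when no session has yet been held, so at that moment they can be applied only as undertakings. Criterion 4 is phrased as permission, and criteria 1 and 6 also look ahead. On that reading both arms pass the same test before allocation and there is no bias.

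This reading is plausible but not secured:

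- Criteria 2, 3 and 5 name conduct, not agreement to it.
- The section says the information document will list the inclusion criteria and, as a separate item, the requirements a teacher must accept. Attendance is placed among the criteria.
- The student criteria beside them require completed questionnaires on three occasions, which cannot be verified until T3. The protocol thus does use inclusion criteria for later conduct.

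It can also be said that analysis sets belong in a SAP, which is not at hand. That is fair, and the lack of an analysis-set rule is not the point here. The point is an eligibility rule that the protocol itself states and words badly.

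Three stronger inferences are tempting but not supported:

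- A reader might infer that non-attending teachers will be removed. The protocol never says so; the harm depends on how the criteria are enforced.
- A reader might infer that losing two teachers leaves 14, below the 15 in the sample size section. That minimum already allows for 40% dropout, so it is not a number that must remain after losses. Fourteen teachers with two classes of at least 14 students would still bring 14 × 2 × 14 = 392 invited students.
- A reader might infer from "Two discussion groups with all PE teachers will be held throughout the study" that controls would sit in discussions of the training and be contaminated. The training section uses the same unqualified wording for the experimental arm alone, and the listed topics are the sessions, the trainers and the follow-up. This is a minor wording conflict.

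The size figures can also be challenged. The individual follow-up takes place at the teacher's own school and is harder to miss. With the five group sessions only, at 95%, the expected loss is 8 × (1 − 0.95^5) = 1.8.

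**Conclusion.** The concern holds in conditional form. Criteria 2, 4 and 5 and the session-questionnaire half of criterion 3 are worded as conduct after randomisation that only experimental teachers can fail before or at T3. Enforced as worded, they would filter one arm on adherence and leave the other unfiltered, and randomisation would no longer protect the comparison for teachers or students. That the bias would favour the program is a judgement about who misses sessions; the protocol gives no data on it.

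The size is unknown. Under assumed independent attendance of 90% to 98%, about 0.9 to 3.7 of 8 experimental teachers would fail over six sessions, and about 0.6 to 2.8 over the four initial ones, against none of 8 controls on the same grounds. If the criteria are applied only as prior commitments, there is no bias, but the text should then say so.

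**What to change.** - Reword criteria 2, 4 and 5 and the session-questionnaire half of criterion 3 as agreement given by every teacher before allocation: to attend the sessions and complete their questionnaires, be recorded and join the focus groups if allocated to the experimental group.
- State that every randomised teacher and their classes remain in the allocated arm whatever the attendance, and that sessions attended are reported as adherence.
- Align criterion 5 and the Focus groups section with the Abstract, Observation and Control group sections, so that focus groups and recordings apply to experimental teachers only.

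The cost is protocol wording. The estimated effect may be slightly smaller, because teachers with imperfect attendance stay in the comparison.

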## **Materials and methods**

### ***Context, design, and randomization***

[figure not shown]
This study will be carried out in a northeast region of Spain [details masked for review process]. PE is mandatory for every secondary school student in Spain. Each student receives two 50-minute coeducational PE lessons per week. Spanish Secondary PE teachers are expected to teach between 18 and 21 hours per week. Typically, the annual teaching plan of PE teachers includes approximately six to eight distinct teaching units per year. These units encompass various content types such as individual, cooperative, and interactive sports and games, as well as body expression, health-related fitness, and outdoor activities, all of which are outlined in the PE curriculum. The academic year lasts from September to June, divided into three terms, each separated by a holiday period (i.e., Christmas and Easter).

A randomized controlled trial design with a mixed-method approach will be carried out. PE teachers agreeing to participate in the trial will be randomly assigned to either the experimental or the control group. Randomization will be conducted using the digital tool available at <https://echaloasuerte.com/>. To prevent contamination of the experimental condition, schools will only participate in one group (i.e., experimental or control). Subsequently, at least two groups of students from each PE teacher will be randomly selected.

This study will comprise two phases: 1) a teacher-training phase and 2) an implementation phase with students. It should be noted that the training program will continue with some individual and group sessions during the implementation phase. Since teachers' and students' perceptions of (de)motivating teaching styles and approaches and other study variables require several months for greater accuracy in their perceptions, the

training program will not start until the second term of the academic year (for more details see Figure 1).

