### **Sample size calculation**

The sample size for this intervention-based study was calculated using R Studio to ensure adequate power in the detection of potential statistically significant effects.

Considering a multi-level design nesting center, PE teacher and group, the sample size calculation was grounded on an anticipated effect size of 0.5, reflecting a moderate impact of the intervention. The power of the study was set at 80% with a significance level (alpha) of 0.05, aligning with common practices in educational research (McConnell et al., 2019).

Acknowledging the inherent structure of this study, an Intra-Class Correlation (ICC) of 0.1 was assumed based on similar educational settings (Hedges & Hedberg, 2007). This ICC estimate accounted for the expected homogeneity within the three levels (class group within PE teacher, PE teacher within center). To accommodate potential participant dropout, particularly among students, we incorporated a 40% anticipated dropout rate into our calculations (e.g., Meerits et al., 2022). The minimum sample size was adjusted to 210 students across 15 PE teachers, averaging 14 students per teacher. This adjustment ensures that our study maintains sufficient statistical power even in the face of anticipated losses, thereby safeguarding the integrity and validity of our findings.

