### ***Analysis plan***

#### ***Quantitative analyses***

Firstly, the effects of the four sessions of the training program on the study variables assessed in teachers will be examined. The overall mean for each of the 11 variables perceived by PE teachers about the quality of the training program (e.g., interaction, innovation, interest, intelligibility, etc.) will also be calculated, representing the mean across the different sessions. A repeated measures analyses of variance (ANOVA) will be used to assess PE teachers' global appreciation of 11 variables related to the quality of the training program (e.g., interaction, innovation, interest, intelligibility, etc.) across the sessions of the training (i.e. within-subject analyses). Accordingly, each of the training sessions will be introduced as an independent variable (i.e. within-subject factor) and repeated measures of the PE teachers-related variables will be entered sequentially as dependent variables.

Secondly, the effects of the intervention implementation in PE lessons on study variables for both teachers and students will also be examined. Levene and Kolmogorov–Smirnov tests will be used to ensure the equality of variances and normal data distribution, respectively ( $p > .05$ ). Cronbach's coefficient will be calculated for each study variable across the three measurements. To examine the effects of the intervention on study variables, a  $3 \times 2$  (time x condition) repeated measures multivariate analysis of covariance (MANCOVA) will be performed for both teachers and students. Age, gender, teaching experience, type of school (public or private), and school location (rural or urban) will be introduced as covariates among teachers, while age, gender, and school grade level will be introduced as covariates among students. Subsequently, to examine intragender differences of the intervention on study variables, a  $3 \times 2 \times 2$  (time x condition x gender) repeated measures MANCOVA will be performed for both teachers and students. The same covariates will be entered as previously analysis, excluding gender. Multiple paired t-tests with Bonferroni correction will be calculated to determine between-group (i.e., experimental-control group) and within-group (i.e., pre-post) differences. Cohen's criteria will be used as indicators of small (.01), moderate

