(.06), and large (.14) effect sizes (Field, 2017). All statistical analyses will be conducted using IBM SPSS Statistics v.25.0. Finally, a longitudinal structural equation model will be used to analyze the predictive relationships between the study variables, allowing for observation of potential differences at the three specific times (i.e., pre-test, middle, and post-test) when data are collected.

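### Student inclusion criterion 2 (questionnaires completed at all three waves) can be judged only at T3 and, applied as written, limits the student comparison to three-wave completers

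*Protocol*

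**What the plan says.** Participants and recruitment states that "the inclusion criteria for students will be: 1) Authorization from parents or legal guardians; 2) Completion of questionnaires of the study variables three times", followed by "3) Regular participation in PE lessons". The section does not say when regular participation is judged. Under Measures, students answer at T1 (before the training), T2 (during implementation) and T3 (at its end); implementation runs from January to the end of May.

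Under Context, design, and randomization, teachers are randomised first. Then: "Subsequently, at least two groups of students from each PE teacher will be randomly selected".

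Sample size calculation states that "we incorporated a 40% anticipated dropout rate into our calculations", presenting the loss as dropout among participants, mainly students. The result is: "The minimum sample size was adjusted to 210 students across 15 PE teachers", or 14 per teacher.

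Under Quantitative analyses, the effect of the intervention is tested with a 3 × 2 (time by condition) "repeated measures multivariate analysis of covariance (MANCOVA) will be performed for both teachers and students". The software is fixed too: "All statistical analyses will be conducted using IBM SPSS Statistics v.25.0".

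**The concern.** An inclusion criterion should be decidable at entry and, in a randomised trial, should not depend on anything allocation can influence. Completion of three questionnaires fails on both counts: it is known only at T3, and the intervention aims to change how students experience PE, which may affect who is still present and responding.

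If the rule is followed, the third hypothesis (benefit to boys and girls in the experimental groups) is tested on students who responded every time, not on the enrolled students of randomised teachers. That gives up part of the protection of randomisation. It also discards answers already given by students who missed one later wave. Raising recruitment to allow for 40% loss restores numbers, but does not correct for who is lost.

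The regular-participation criterion raises the same question if it is judged after T1.

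**Working it through.** **1. The plan's own figure.** Inputs from Sample size calculation: effect size 0.5 (taken as a standardised difference, SD 1), power 80%, alpha 0.05 (two-sided assumed), dropout 40%.

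- Per arm: 2 × (1.960 + 0.842)² / 0.5² = 62.8, rounded up to 63; total 126.
- After dropout: 126 / (1 − 0.4) = 210, the stated minimum.

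The allowance is therefore sized to leave 126 students. (This reproduction uses no design effect for the stated ICC of 0.1. That is a separate matter and plays no part here.)

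**2. Students excluded, if dropout means missing at least one wave.**

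- 0.4 × 210 = 84 excluded; 0.6 × 210 = 126 kept.
- 126 / 15 = 8.4 per teacher instead of 14.
- At the recruitment minimum of 16 teachers × 2 groups × 14 students = 448, if all enrolled: 0.4 × 448 ≈ 179 excluded and 269 kept.

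**3. Records discarded.** Of 210 students answering at T1, 84 are lost by T3 and none returns. A completer analysis uses 3 × 126 = 378 records.

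| When the 84 are lost | Records collected | Discarded |
|---|---|---|
| All before T2 | 210 + 126 + 126 = 462 | 84 (18.2%) |
| Half before T2, half after | 210 + 168 + 126 = 504 | 126 (25.0%) |
| All after T2 | 210 + 210 + 126 = 546 | 168 (30.8%) |

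**4. How bias arises.** Let m be the dropout proportion in an arm and g the completer minus non-completer mean. The full mean is (1 − m) × completer mean + m × non-completer mean, so the completer mean exceeds it by m × g. The bias in the between-arm difference is mE × gE − mC × gC, where E is experimental and C control. It is zero if both m and g are equal across arms; in general it is not if either differs.

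Illustration only: with m = 0.4 in both arms, the bias is 0.4 × (gE − gC). Assumed gap differences of 0, 0.1, 0.2 and 0.3 SD give 0, 0.04, 0.08 and 0.12 SD, in either direction, against the planned 0.5. The gap differences are not document figures.

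**5. The second route to the same set.** A repeated-measures MANCOVA in its standard SPSS form needs the full set of waves for each person and by default drops anyone missing one. Removing criterion 2 and leaving the analysis as it is would leave the same 126 students.

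**The case against.** **There is no contradiction in the numbers.** This stands. Since 126/0.6 = 210, the plan can be read as recruiting 210 so that 126 complete. A reader might infer that the sample size and the criterion conflict arithmetically; they do not. What remains is definitional: one section counts dropouts as participants, the other makes them ineligible. On the recruit-to-complete reading, criterion 2 is really an analysis-set rule, and the comparison is still completers only.

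**The criterion may be meant as a commitment.** This is possible, and no passage says that students who miss a wave are removed. But the student wording is completion, not willingness, and nothing in the student text frames it as an undertaking given in advance. If that was the intention, one sentence settles it.

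**Listwise deletion is inferred.** This also stands. It is the default of the named procedure, not a stated rule, and imputation before the MANCOVA would be compatible with the text. An SAP, which is not at hand, could specify it. However, an SAP that brought partial responders back would conflict with the criterion as written. The planned longitudinal structural equation model could use partial data, but it addresses predictive relationships, and the criterion would bind it too.

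**Dropout is not defined.** This is correct. A student absent only on the T2 day fails criterion 2 without having left the study, so 84 depends on equating dropout with a missed wave.

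**T1 is not a clean anchor.** This is correct as well. Student groups are selected after teachers are allocated, so T1 may itself follow allocation. The fix allows for this.

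**Conclusion.** The point holds and should be corrected, because it concerns the main student comparison and two things that the Protocol itself fixes: an eligibility rule and an analysis model. Criterion 2 is a post-randomisation outcome; applied as written, it confines the student comparison to three-wave completers.

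If dropout means missing a wave, this excludes about 84 of 210 students. If, in addition, nobody returns, it discards 18% to 31% of collected student-wave records.

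A reader might infer that the result will be biased by up to 0.12 SD. The document does not support that: the figure rests on assumed gaps, and neither the size nor the direction of any bias can be derived. What can be said is that the completer comparison is open to bias if dropout or the gap differs by arm.

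A reader might also infer that the similarly worded teacher criteria filter the experimental arm on adherence. The text says only that "various inclusion criteria will be considered for the final selection"; it nowhere says that teachers who fall short are removed. They form no part of this point.

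**What to change.** - Delete student criterion 2, or reword it as an expectation explained at consent, and state that students who miss a wave stay enrolled.
- Judge regular PE participation at or before T1, preferably before allocation is known, by the same rule in both arms.
- Analyse all enrolled students of randomised teachers in the allocated arm, with a model that keeps partial responders. One option is a linear mixed model per outcome with time × condition and random effects for student, class and teacher, adding centre where a centre has more than one teacher. Centre, teacher and class group are levels that the sample size section already names.
- Report dropout by arm, and keep the three-wave completer set as a sensitivity analysis only.

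The cost is a few sentences on eligibility and a change of model. No new data are needed, and the named package has a mixed-model procedure. The downsides are more analysis work, the loss of a single multivariate test (so multiplicity across outcomes needs handling), and a remaining assumption that data are missing at random given what was observed.
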